### **7.2 OBJECTIVES**

The primary objective for this study is as follows:

- To evaluate the overall safety and tolerability of emicizumab administration, in all patients and in subgroups determined by age and status of inhibitor as well as by severity for patients without inhibitors

Primary safety endpoints:

- Frequency and incidence of TEs, TMA, anaphylaxis

The secondary objectives for this study are as follows:

- To evaluate frequency and incidence of any adverse events reported to the PedNet Registry in patients treated with emicizumab, overall and in subgroups determined by age and status of inhibitor as well as by severity for patients without inhibitors

Secondary safety endpoints:

- Any AEs reported to PedNet Registry

- To describe the bleeding profile of patients treated with emicizumab, overall and in subgroups determined by age and inhibitor status

Effectiveness endpoints:

- ABR for treated\* bleeds and percentage of patients with zero treated bleeds
- ABR for joint bleeds and major bleeds
- Bleed count for soft tissue bleeds and minor bleeds

\*As per PedNet data collection, all bleeds reported are treated bleeds

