PedNet emicizumab specific report includes patients who are treated with emicizumab. The following data includes in the reports: number of patients treated with emicizumab, duration of emicizumab exposure, number of TE, TMA, anaphylaxis, and any other AEs,

ABR for treated bleeds, percentage of zero bleeds, ABR for joint bleeds, ABR for soft tissue bleeds, ABR for major or minor bleeds, number of patients which have used bypassing aPCC agents when treated with emicizumab, number of patients which have used FVIII products when treated with emicizumab, the number of patients used rFVII when treated with emicizumab and detailed data for patients who have developed TE, TMA or and anaphylaxis. Based on the PedNet annual report, the MAH produces the PASS report annually with the following information grouped by age and status of inhibitor as well as by severity for patients without inhibitors and/or include the results in the annual PBRRER depending on the time of availability of PedNet reports:

- Number of patients exposed to emicizumab (directly from PedNet report)
- Number of patients exposed to emicizumab who experienced TE, TMA, and anaphylaxis (calculated from PedNet report)
- Proportion and incidence of each AE of TE, TMA, and anaphylaxis among patients receiving emicizumab (calculated based on information from PedNet report)
- Number of patients exposed to emicizumab and each of the following drugs: aPCC, rFVIIa, FVIII (directly from PedNet report)
- Number of patients exposed to emicizumab and each of the following drugs: aPCC, rFVIIa, FVIII, who experienced TE, TMA, and anaphylaxis (calculated from PedNet report)
- Proportion of TE and of TMA among patients exposed to emicizumab and each of the following drugs: aPCC, rFVIIa, and FVIII (calculated based on information from PedNet report)
- Number of any other AE and number of patients with any other AE (including inhibitor development, unexpected poor efficacy, local subcutaneous reactions) reported to PedNet Registry (directly from PedNet report)
- ABR for treated bleeds, percentage of zero bleeds, ABR for joint bleeds and ABR for major bleeds (directly from PedNet report)
- Bleeds count for soft tissue bleeds and minor bleeds

PedNet performs annual data extractions in January of each year. Following each data extraction, PedNet group analyzes the data according to this protocol and provide the MAH with Annual Emicizumab-Specific Reports.

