## 8.7 DATA ANALYSIS

### Data transformation

The MAH will receive aggregate level data of patients treated with emicizumab from the PedNet Registry on an annual basis.

Based on the number of patients, number of AEs, and exposure to emicizumab provided by the Registry, the MAH will perform analyses of frequencies/incidence of AEs overall and grouped by age and status of inhibitor as well as by severity for patients without inhibitors. The youngest age group will be newborn (birth to 28days). Other age groups include: 29 days-<6 months, 6 months-<2 years, 2 years-<6 years, 6 years-<12 years, 12 years-18 years. The MAH will report ABR for treated bleeds, percentages of zero bleeds, ABR for joint bleeds and major bleeds overall and grouped by age and status of inhibitor as well as by severity for patients without inhibitors as sent by PedNet registry. ABRs for soft tissue bleeds and minor bleeds is not calculated by PedNet and therefore only the number of bleeds will be presented.

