### **8.7.2            Secondary analyses:**

- Annual incidence proportion of AE of interest (TMA, TE, and anaphylaxis) among patients exposed to emicizumab will be estimated as the number of patients who were treated with emicizumab and developed the AE, divided by the number of patients who are exposed to emicizumab. The incidence proportion will be calculated overall and by age and status of inhibitor as well as by severity for patients without inhibitors.
- For each AE of interest (TMA, TE, and anaphylaxis), the following proportions will be calculated, together with the corresponding 95% confidence intervals:
  - Annual incidence proportions of the AE among patients treated with emicizumab and concurrently with each of the following drugs: aPCC, rFVIIa, and FVIII product.
- Annual number and percentage of each of the other adverse events reported to PedNet will be presented. Currently, in addition to TE, TMA, and anaphylaxis, these events may include: new inhibitors, allergic reactions, local subcutaneous reaction, other AEs including unexpected poor efficacy.
- ABRs: Estimates for the ABR are based on a negative-binomial model adjusted for age group and inhibitor status. The negative-binomial models each use the “total number of bleeds” (for each specified type of bleed) as the outcome and the model is offset by the “total duration of follow-up” since first exposure to emicizumab.

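### The objective promises incidence of any adverse event, but outside TE, TMA and anaphylaxis the specified outputs are counts and percentages with no person-time

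*Protocol*

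**What the plan says.** The promise appears in two places. Section 7.2 sets the secondary safety objective: "To evaluate frequency and incidence of any adverse events reported to the PedNet Registry in patients treated with emicizumab", overall and by age, inhibitor status and, for patients without inhibitors, severity. The opening of 8.7 names the inputs, "Based on the number of patients, number of AEs, and exposure to emicizumab provided by the Registry", and continues that "the MAH will perform analyses of frequencies/incidence of AEs overall and grouped by age and status of inhibitor", again with severity. That sentence is not limited to particular events.

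The outputs are set in three places.

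- **Section 8.1** says "the MAH produces the PASS report annually with the following information grouped by age and status of inhibitor", and by severity. Within that list the three primary events get "Proportion and incidence of each AE of TE, TMA, and anaphylaxis among patients receiving emicizumab". Other events get "Number of any other AE and number of patients with any other AE".
- **Section 8.7.1** defines the person-year rate, its exposure formula and its interval for TE, TMA and anaphylaxis. It says that additional events will be included but names no measure for them.
- **Section 8.7.2** says for the rest: "Annual number and percentage of each of the other adverse events reported to PedNet will be presented". It lists new inhibitors, allergic reactions, local subcutaneous reactions and other events, including unexpected poor efficacy.

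The Data Analysis part of the synopsis (section 3) promises 95% confidence intervals for the proportions of patients with each type of adverse event, naming the three primary events as examples.

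**The concern.** The study's secondary safety question covers every recorded adverse event. The plan announces incidence for all of them, yet defines a rate for only three. For the others, the two places that fix the output stop at counts and percentages.

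This matters because patients start emicizumab at different times over a six-year study, and section 6 dates the EU approvals for non-inhibitor patients almost four years apart (11 March 2019 for severe disease, 23 January 2023 for moderate disease). A percentage of patients affected rises with time on drug. If exposure differs between strata, the one with shorter exposure looks safer at the same underlying rate. The moderate stratum could be affected in this way, and section 4 says the amendment added severity so that safety in moderate disease could be reported.

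New inhibitor development raises a further question. A patient who already has an inhibitor is not at risk of a new one, and 8.7.2 does not say whose percentage is meant.

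**Working it through.** **1. Objective against output, for adverse events other than the three primary ones**

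| Place | Measure | Person-time | Subgroups | Interval |
|---|---|---|---|---|
| 7.2 | frequency and incidence | not stated | yes | not stated |
| 8.7 opening | frequencies/incidence | yes, exposure is an input | yes | not stated |
| 8.1 list | number of events, number of patients | no | yes | no |
| 8.7.1 | included, no measure named | rate defined for the three primary events only | – | – |
| 8.7.2 bullet | annual number and percentage | no | not stated | not stated |
| Synopsis, Data Analysis | proportion, each type of event | no | age groups named | 95% CI |

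No place says how an exposure-based incidence is to be calculated for other events.

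**2. How far a percentage can move at a constant rate**

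The protocol gives no counts of other events and no exposure by stratum, so no trial figure can be computed. The rates and exposures here are assumptions. With a constant rate r and exposure T years, the cumulative percentage affected is 1 − exp(−rT).

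| Assumed rate per person-year | T = 0.5 | T = 1 | T = 3 |
|---|---|---|---|
| 0.02 | 1.0% | 2.0% | 5.8% |
| 0.10 | 4.9% | 9.5% | 25.9% |
| 0.20 | 9.5% | 18.1% | 45.1% |

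For example, 1 − exp(−0.10 × 0.5) = 4.9% and 1 − exp(−0.10 × 3) = 25.9%. If annual means within one reporting year, T cannot exceed 1. The largest contrast in the table is then 0.5 against 1 year, roughly two-fold (4.9% against 9.5% at 0.10).

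**3. The same check with the protocol's own formula**

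Take 100 patients, 10 of them with an event, so 10% throughout. The 8.7.1 formula gives person-years = 100T − 10 × T/2 = 95T.

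- T = 0.5: 10/47.5 = 0.211 per person-year
- T = 1: 10/95 = 0.105
- T = 3: 10/285 = 0.035
- T = 5: 10/475 = 0.021

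One percentage is thus compatible with a ten-fold range of rates.

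**4. New inhibitors**

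Section 8.5 reports 80 patients with inhibitors, 132 without and 4 unknown (216 in all) at the last interim. If that is status when emicizumab started, dividing by all patients instead of those at risk lowers the percentage by the share not at risk:

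- unknowns excluded: 80/212 = 37.7%
- unknowns counted as inhibitor-free: 80/216 = 37.0%
- unknowns counted as having an inhibitor: 84/216 = 38.9%

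This concerns only an overall figure. Within the non-inhibitor stratum the denominator is already the at-risk group.

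**The case against.** The case for leaving the text alone is that this is a wording mismatch in a descriptive secondary objective. The opening of 8.7 does promise an exposure-based analysis. Section 8.7.2 does not say that number and percentage are all that will be shown. It also uses the term incidence proportion for patients with an event over patients exposed, so a percentage can be read as an unadjusted form of incidence. Denominators for single secondary events are ordinary content for an analysis plan that is not at hand.

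Much of this stands, and it rules out several stronger readings that a reader might infer:

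- *No incidence of other events is planned.* The 8.7 opening says otherwise. The defect is that the specific outputs do not carry it through.
- *Subgroups and intervals are missing altogether.* The whole 8.1 list is grouped by age, inhibitor status and severity, and the synopsis promises intervals for proportions of each type of event. Only the 8.7.2 bullet is silent on both.
- *Exposure is known to be very unequal.* No passage reports exposure by stratum. Staggered entry and the two approval dates make a difference plausible, no more.
- *There is a five-fold distortion.* The contrast between 0.5 and 3 years needs cumulative percentages and assumed exposures, and the word annual may exclude it.
- *The new-inhibitor percentage uses the wrong denominator.* The protocol states no denominator for it, and section 8.5 does not say when the 80 patients were classified.

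The objection does not remove the central point. The protocol itself fixes the output for other events, and that output differs from what its objective and its analysis section promise.

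**Conclusion.** The mismatch holds. Sections 7.2 and 8.7 promise incidence of any adverse event by subgroup, while 8.1, 8.7.1 and 8.7.2 define an exposure-based rate for three events only. Read literally, the specified outputs do not fully answer the secondary safety objective.

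The size of the consequence cannot be taken from the protocol. It depends on how far exposure differs between strata and on what annual means. Under cumulative percentages and the assumed rates, the contrast between 0.5 and 3 years is about five-fold; within a single reporting year it is about two-fold at most between 0.5 and 1 year. The 37% to 39% relative understatement for new inhibitors applies only if all patients form the denominator and the interim split is baseline status, and neither is stated.

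The change is worth making because section 8.1 already lists the number of patients with other events, and section 8.7.1 has the registry supply the number treated and the mean exposure days.

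**What to change.** In 8.7.2 and in the 8.1 list, extend the person-year incidence rate to other adverse events: patients with a first event divided by person-years of emicizumab exposure, with an exact Poisson 95% confidence interval. Report it overall and by the same age, inhibitor and severity groups, beside the number and percentage. Section 8.7.1 names a binomial interval for its rates; that wording should not be carried over, because the denominator here is person-time. State in the 8.7.2 bullet whether annual means within a reporting year or cumulative to the extraction date.

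For new inhibitor development, base the overall figure, both numerator and denominator, on patients without an inhibitor at the start of emicizumab. Section 8.3.2 already makes inhibitor status a baseline variable at that point.

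The cost is slightly longer tables. The registry may also need to supply exposure for the inhibitor-free group. No new collection of adverse event data is needed.

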### **DATA ANALYSIS**

General principles for data analysis are provided below.

Safety analyses will be conducted in all patients overall and in subgroups defined by age and status of inhibitor as well as by severity for patients without inhibitors, using all authorized emicizumab dosing regimens. Proportions of patients developing each type of AE (e.g., TE, TMA, and anaphylaxis) are calculated along with the corresponding 95% CIs, and are reported for all patients as well as in age-defined subgroups including newborns with or without inhibitors.

Bleed outcomes analyses will be conducted in all patients overall and in subgroups defined by age and status of inhibitor as well as by severity for patients without inhibitors. Mean ABR with standard deviation and percentage of patients with zero bleeds are reported overall and in subgroups defined by age and status of inhibitor as well as by severity for patients without inhibitors. Summary statistics are provided overall and for the relevant subgroups.

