## **8.5 STUDY SIZE**

The sample size depends on the approval and uptake of emicizumab in the countries with centers participating in the PedNet Registry. As of January 2019, PedNet enrolled 1795 patients with hemophilia A, of which 1173 patients had severe disease, 225 patients had moderate disease and 397 had mild disease. Of the patients with severe disease, 351 patients had inhibitor diagnosed between 2000 and 2019.

Assuming a constant sample size of patients with severe disease in the registry (N=1173 with severe disease regardless of FVIII inhibitor and N=351 with inhibitor), and assuming that at least 50% of these patients receive emicizumab during the 6 years of the study, the anticipated sample size is expected to be n=587 for patients with severe disease and n=176 for patients with inhibitor at the end of this 6-year study.

No data about inhibitor status is available at this stage for patients with moderate disease. Assuming a constant sample size of patients with moderate disease in the registry (N=225 with moderate disease regardless of FVIII inhibitor), and assuming that at least 15% of these patients receive emicizumab during the 6 years of the study, the anticipated sample size is expected to be n=34 for patients with moderate disease.

The table below presents possible sample sizes with the average adoption of the drug varies between 15%–75% for severe patients and 5-25% for moderate patients during the study.

The MAH acknowledges that these estimates may change if the total number of patients enrolled in the registry changes significantly during the study time. As per last interim CSR (28-Sep-2022), a total of 266 patients enrolled since the beginning of the PedNet Registry up until the clinical cutoff date of 31 December 2021 were reported to have started treatment with emicizumab (regardless of the severity). Of these, 216 patients had updated follow-up data until 31 December 2021 and were included in the CSR (80 patients with inhibitors, 132 patients without inhibitors, and 4 patients with unknown inhibitor status).

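### The descriptive ABR in Section 8.7.2 rests on an adjusted negative-binomial model that conflicts with the synopsis and does not cover every ABR the protocol promises

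*Protocol*

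**What the plan says.** Section 7.2 states the aim as "To describe the bleeding profile of patients treated with emicizumab, overall and in subgroups determined by age and inhibitor status". The synopsis version of this objective, and Section 8.7, add severity for patients without inhibitors.

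The protocol then describes the ABR in two ways:

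- Synopsis, Data Analysis: "Mean ABR with standard deviation and percentage of patients with zero bleeds are reported overall and in subgroups defined by age and status of inhibitor", and also by severity in patients without inhibitors.
- Section 8.7.2: "Estimates for the ABR are based on a negative-binomial model adjusted for age group and inhibitor status". The outcome is the bleed count of each type, offset by follow-up "since first exposure to emicizumab".

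Section 8.7 (Data transformation) sets six age groups. It says "The youngest age group will be newborn (birth to 28days" days) and then "Other age groups include: 29 days-<6 months, 6 months-<2 years, 2 years-<6 years, 6 years-<12 years, 12 years-18 years". ABRs are to be reported in these groups, by inhibitor status and by severity in patients without inhibitors, as the registry sends them. Section 8.5 describes the patients in the last interim report as "80 patients with inhibitors, 132 patients without inhibitors, and 4 patients with unknown inhibitor status".

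**The concern.** A covariate-adjusted model serves a comparison between groups, and none is planned here. A descriptive ABR should state how often the treated children bled per year of follow-up. A model with covariates does not give one overall rate until someone chooses how to average over them, and common choices can differ materially.

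The model as stated also does not match the tables the protocol requires. Severity is absent, unknown inhibitor status has no level, and nothing is said about a band without bleeds. The ABR is the study's only effectiveness rate. The sponsor receives aggregate results only, so it could not refit the model to find out which quantity it had been sent.

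**Working it through.** **Figures in the protocol.** It states no ABR, so there is none to reproduce. The study sizes do reproduce: 0.50 × 1173 = 586.5 (587 severe) and 0.15 × 225 = 33.75 (34 moderate), together 621. The interim total is 80 + 132 + 4 = 216, and 4/216 = 1.9%.

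**Required output against the stated model.**

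| Required ABR | Available from the 8.7.2 model? |
|---|---|
| Overall | Only after choosing an averaging rule |
| By age, by inhibitor status | Yes, with the same choice |
| By severity, no inhibitor | Not without a separate fit |
| Unknown inhibitor status | Dropped, or given a level of their own |
| Age band with no bleeds | No finite log-rate or Wald interval |

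**How much the read-out matters.** The protocol gives no band sizes or bleed rates, so these are assumed:

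- 212 patients with known status in bands of 3/8/31/55/70/45, youngest first;
- rates without inhibitor of 0.3/0.3/0.5/0.6/0.6/0.7 per year;
- inhibitor rate ratio 1.3, with the same inhibitor share (80/212 = 0.377) and mean follow-up in every band.

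Results:

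- Cohort rate: size-weighted mean 125.3/212 = 0.591, times (1 + 0.377 × 0.3) = 1.113, gives **0.66**.
- Equal-weight adjusted mean: geometric mean of the six rates 0.474, times √1.3 = 1.140, gives **0.54**, and 0.540/0.658 = 0.82 (18% lower).
- At covariate means: size-weighted geometric mean 0.582, times 1.3^0.377 = 1.104, gives **0.64** (2% lower).
- Predictions averaged over the treated patients: **0.66** if the model holds. In simulation of this scenario the median ratio to the crude rate was 0.99 to 1.00.

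With inhibitor ratios of 1 to 2 and steeper age gradients, the equal-weight value is 18% to 26% lower and the covariate-mean value 1% to 9% lower. With no age effect, the equal-weight value is 0% to 3% higher.

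**A band with no bleeds.** One simulated data set had 216 patients in bands of 4/10/30/60/70/42, inhibitor ratio 1.5, dispersion 1.5 and no newborn bleeds. It gave these overall values:

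- crude rate 1.16;
- mean of individual ABRs 1.28;
- model averaged over patients 1.21 (time-weighted 1.18);
- reference cell 0.94;
- at covariate means 0.44;
- equal-weight mean 0.0005.

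The last two are artefacts. The newborn coefficient runs towards minus infinity (−44, standard error about 10^7, not converged) and pulls down every log-scale average. The other bands' estimates and the patient-averaged value stay finite.

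**Subgroups.** With roughly multiplicative effects, averaging over the observed mix stays close to crude (12 to 18 years: 2.21 against 2.16). With an assumed age-by-inhibitor interaction, a model without that term misses: inhibitor patients 2.38 against 2.85 crude, and 12 to 18 years 3.04 against 3.50.

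**Chance of an empty band.** For n patients followed t years at rate r with dispersion k, P(no bleeds) = (1 + k·r·t)^(−n/k). Scaling the assumed bands to 621 puts 9 and 23 patients in the two youngest. With t fixed at 1.5 and no inhibitor effect:

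| Bleed type | k | r, two youngest bands | P, n = 9 | P, n = 23 | Either band |
|---|---|---|---|---|---|
| All | 1.5 | 0.3 | 1.675^−6 = 0.045 | 0.0004 | 0.05 |
| Joint | 2 | 0.1 | 1.30^−4.5 = 0.307 | 0.049 | 0.34 |
| Major | 2 | 0.05 | 1.15^−4.5 = 0.533 | 0.200 | 0.63 |

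With follow-up spread over 0.3 to 2.7 years (mean 1.5) and the inhibitor ratio of 1.3 included, the figures become about 0.04, 0.31 to 0.32, and 0.59. At the 212 interim patients of known status they were about 0.39, 0.75 and 0.92.

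**The case against.** A reader might infer that the overall ABR, as written, is not the bleeding rate of the treated children. The document does not support that. Section 8.7.2 names a model, covariates and an offset; it prescribes neither equal weights nor prediction at covariate means. Averaging predictions over the treated patients recovers the crude rate almost exactly, and the averaging rule could properly sit in an analysis plan that is not shown.

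Nor does the document support a claim that the ABR is biased in the drug's favour. The 18% needs both equal weighting and an assumed age gradient, and it vanishes without the gradient. It is also too strong to say that the model breaks down: the trouble is confined to the empty band and to log-scale averages that include it. The 39%, 75% and 92% figures belong to the interim size, not the planned size. That the model uses the six reporting bands is itself an inference, since Section 8.7.2 says only age group.

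Finally, an intercept-only model also has no finite log-rate in a group without bleeds, so adjustment alone does not cause that problem.

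All of this stands, and it limits the size of the point. It does not remove the conflict between the synopsis and Section 8.7.2, the missing severity factor, the unplaced unknown-status patients, or the lack of a usable interval for an empty band.

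**Conclusion.** The point holds as a mismatch within the protocol. The synopsis and Section 8.7.2 describe different ABRs, and the model in 8.7.2 cannot by itself supply every ABR that Section 8.7 requires.

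The effect on the overall figure depends on the read-out: about 18% lower, 2% lower or essentially nil under the assumed inputs. An empty age band at the planned 621 patients is unlikely for all treated bleeds (about 4%) but plausible for joint (31%) and major bleeds (59%). These rest on assumed band sizes, rates, dispersion and 1.5 years' mean follow-up, and on the six reporting bands being those in the model. Larger young bands or longer follow-up would lower them. Unknown inhibitor status affects 1.9% of interim patients, so its weight is small. This is a worthwhile, inexpensive correction, not a threat to the study's primary safety aim.

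**What to change.** In Section 8.7.2:

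- Define the descriptive ABR for each modelled bleed type as total bleeds divided by total patient-years (or an intercept-only negative-binomial estimate with log follow-up as offset). Calculate it for all patients and separately within each reported group, including severity in patients without inhibitors.
- Where a group has no bleeds, report 0 with an exact Poisson 95% interval, whose upper limit is 3.69 divided by patient-years. For example, 9 patients with 1.5 years each give 3.69/13.5 = 0.27 per year.
- Include patients with unknown inhibitor status in the overall ABR.
- Keep the adjusted model only as supportive, for rate ratios or with predictions averaged over the observed patients.

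Align the synopsis with this definition, so that one quantity is called the ABR throughout.

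The cost is a change of wording and simpler code at the registry, with no new data. Intervals in small subgroups will be somewhat wider, because they no longer borrow strength through common covariate effects.

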## **8. RESEARCH METHODS**

### **8.1 STUDY DESIGN**

This is a non-interventional (NI) secondary data use Post-Authorization Safety Study (PASS) relying on data collected as part of the PedNet Registry. PedNet Registry will extract data (e.g., all variables) indicated in this protocol, perform the statistical analysis and provide results to the Marketing Authorization Holder (MAH) as an aggregated report. Based on this, the MAH will generate an annual PASS report and submit it to the Pharmacovigilance Risk Assessment Committee (PRAC) and/or include the annual report in the periodical benefit risk evaluation report (PBRER) depending on the time of availability of the reports.

PedNet is a multicenter, observational research database that includes patients with FVIII/IX levels < 25 IU/dL born after 1 January 2000 and treated in one of the participating Hemophilia Treatment Centers (HTCs). At the time of protocol amendment, 32 centers from 19 countries are participating in the Registry. The goal of the Registry is to include full cohorts of all consecutive patients diagnosed and treated in each center of which information on treatment and outcomes (e.g., inhibitor development, bleeds) is collected from the time of hemophilia diagnosis or time of first treatment. To prevent selection bias, patients referred to a center after development of inhibitors are not included in the database.

Data included in the Registry is collected using electronic case report forms (eCRFs). Baseline data that pertains to mode of delivery, neonatal events, diagnostic symptoms, FVIII/IX gene mutation, and family history of hemophilia and inhibitors is collected. All centers collect detailed data on treatment and outcomes (including inhibitor development and bleeds) of patients with hemophilia during the first 50 days of exposure to coagulation factor concentrate products. Following this, the centers continue to collect information at least annually until the patient reaches the age of 18. Additional information are collected regarding surgeries, hospitalizations, and AEs.

A similar level of detail is collected for patients treated with emicizumab prophylaxis. When patients treated with emicizumab receive coagulation factor concentrate products, the type of the products is recorded. It is therefore possible to evaluate the relationship between the use of FVIII/BPAs and development of TE/TMA events for patients treated with emicizumab prophylaxis.

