### 8.7.1 Primary Analyses

The primary AEs are TE, TMA, and anaphylaxis. Additional AEs including inhibitor development and unexpected poor efficacy will be included as they are collected by PedNet Registry.

Adverse events collected in PedNet are not collected according to MedDRA classification. Most events are collected according to pre-specified lists; however, free-text fields are also available for each event. Whenever possible, AEs will be reclassified by Roche according to MedDRA PT level using the most current MedDRA version.

Primary analyses: For each AE of interest (TMA, TE, and anaphylaxis), the following analysis will be performed overall and grouped by age and status of inhibitor as well as by severity for patients without inhibitors:

- Annual incidence rate of the AE among patients exposed to emicizumab will be estimated as the number of patients who were treated with emicizumab and developed the AE, divided by the person years of emicizumab exposure. The numerator will be calculated using report from PedNet.
- PedNet will provide number of patients treated with emicizumab and emicizumab mean exposure days, which will be used to calculate the person years of emicizumab exposure using the following formula:

Person years of emicizumab exposure=[number of patients exposed to emicizumab×mean emicizumab exposure time in days–number of patient exposed to emicizumab and had event×(mean emicizumab exposure time in days/2\*)]/365.25

\*Note that this calculation accounts for patients who are censored in the study once they have experienced an adverse event (event is imputed to happen after half the exposure time).

Exact binomial 95% confidence intervals will be calculated for each incidence rate.

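### The ABR model in Section 8.7.2 runs on all follow-up from first dose with no end at discontinuation, so read literally it mixes off-drug bleeds and time into the emicizumab ABR

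*Protocol*

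**What the plan says.** Section 8.7.2 defines the ABR analysis: "Estimates for the ABR are based on a negative-binomial model adjusted for age group and inhibitor status". The outcome is the total number of bleeds of the given type, and "the model is offset by the “total duration of follow-up” since first exposure to emicizumab". The window has a start ("since first exposure to emicizumab") but no stated end, and bleeds are not restricted to time on drug.

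For the adverse events of interest, Section 8.7.1 uses a different denominator: the number of patients with the event is "divided by the person years of emicizumab exposure".

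Section 8.1 describes how long the registry observes a child: "the centers continue to collect information at least annually until the patient reaches the age of 18". The same section lists the contents of the registry's emicizumab report, including "number of patients treated with emicizumab, duration of emicizumab exposure".

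The data analysis part of the synopsis describes the bleed results differently: "Mean ABR with standard deviation and percentage of patients with zero bleeds are reported overall". It names no model, and Section 8.7.2 names no mean or SD.

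**The concern.** The objective that the ABR serves (Section 7.2) is the bleeding profile of patients treated with emicizumab. If a child stops emicizumab and stays in the registry, the offset as worded keeps running, and the bleed count with it, under whatever treatment follows. The resulting rate is a blend of on-drug and off-drug bleeding.

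The protocol distinguishes exposure time from follow-up time and uses the wider of the two only for the ABR. Bleeding and safety results in the same annual report would then rest on different kinds of person-time.

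The sponsor could not correct this afterwards. Under Section 8.7 it reports the ABR as the registry sends it, and under Section 8.8 it receives no individual patient data. The instruction to the registry therefore has to be right in the protocol.

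**Working it through.** **No figure to reproduce.** The protocol gives no expected ABR, discontinuation share or precision target for bleeds. The check is a comparison of texts, followed by an illustration on assumed inputs.

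**Texts side by side**

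- Start of the ABR window (8.7.2): first emicizumab exposure.
- End of the ABR window (8.7.2): not stated; the offset is all follow-up.
- Meaning of follow-up elsewhere: collection to age 18 (8.1), and in 8.5 data updated to the clinical cutoff of 31 December 2021. Neither is tied to emicizumab use.
- Denominator for adverse-event rates (8.7.1): emicizumab exposure time.
- Availability of exposure duration: it is in the registry report (8.1).

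The literal rule therefore includes time after stopping, and the information needed for an on-drug rate is already collected in some form.

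**Size, all inputs assumed.** Let *f* be the share of follow-up after first dose that is spent off drug, λ the on-drug bleed rate and *r* the ratio of off-drug to on-drug rate. Over total time *T*:

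reported rate = [(1 − f)·T·λ + f·T·r·λ] / T = λ·[(1 − f) + f·r]

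so reported ABR / on-drug ABR = (1 − f) + f·r.

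| r | f = 2% | f = 5% | f = 10% | f = 20% |
|---|---|---|---|---|
| 0.5 | 0.99 | 0.975 | 0.95 | 0.90 |
| 1 | 1.00 | 1.00 | 1.00 | 1.00 |
| 2 | 1.02 | 1.05 | 1.10 | 1.20 |
| 5 | 1.08 | 1.20 | 1.40 | 1.80 |

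For example, 0.80 + 0.20 × 5 = 1.80 and 0.80 + 0.20 × 0.5 = 0.90. The formula is exact for total bleeds over total time. A fitted negative-binomial model weights patients somewhat differently, so the table is an approximation to it. Ending bleeds and offset at the end of exposure sets f = 0 and returns a ratio of 1.00.

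**Does the estimator matter?** A simulation compared the mean of individual ABRs with the negative-binomial rate. Its assumptions were 216 patients (the number in the last interim report, Section 8.5), mean rate 1 per year, dispersion 2, follow-up uniform from a minimum of 0.02, 0.1 or 0.25 years up to 3 years, and 200 replicates each. Both estimators centred on about 1.0. Within a data set they differed on average by 0.042, 0.028 and 0.020 for the three minimum follow-ups. The SD of individual ABRs was about 1.7 to 1.9. Under a constant rate, then, the choice makes little difference to the point estimate, and the SD describes spread between patients.

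**The case against.** **The protocol does not say that off-drug bleeds are counted.** It gives a start and is silent on the end, and an end-of-window rule for a secondary rate may be left to a statistical analysis plan, which is not shown. This stands in part: inclusion follows from the literal wording together with the length of registry follow-up, and is not an explicit statement. But Section 8.7.2 does more than leave a gap. It names a specific offset, all follow-up, where Section 8.7.1 names exposure.

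**Counting all follow-up from first dose is a recognised choice, and stopping the clock at discontinuation has its own bias.** If children stop because they bleed, censoring at the end of exposure is informative. The protocol anticipates such cases, since unexpected poor efficacy is a recorded event. This stands, and is the reason to report both versions.

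**The safety rates do not define a single period that the ABR could adopt.** Section 8.7.1 subtracts half the mean exposure for each patient with the event, separately by event type, and does not say when exposure ends. This stands. The end date must be defined for the ABR itself.

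**Mean with SD in the synopsis is not a rival estimator.** That part of the synopsis sets out general principles, and a descriptive summary can stand beside a model estimate. A reader might infer that the protocol offers two competing answers, or passes off the SD as the precision of the ABR. It does neither. What remains is a small misalignment between the synopsis and Section 8.7.2.

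**Conclusion.** The point holds as a question of the observation window for a secondary effectiveness endpoint. As worded, the ABR offset is not confined to emicizumab treatment, differs in kind from the safety denominator, and does not match the stated objective.

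A reader might infer that the ABR will be overstated, perhaps greatly. With 10% of follow-up off drug and bleeding at 3 per year off drug against 0.5 on drug, the result would be 0.9 × 0.5 + 0.1 × 3 = 0.75, or 50% too high. That requires a sixfold rate ratio, and the documents support neither input. Over the assumed range (2% to 20% off drug, rate ratio 0.5 to 5), the reported ABR is 0.90 to 1.80 times the on-drug value. The direction depends on what follows emicizumab. The effect is nil if the rates are equal or if nobody stops while still followed.

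The primary rates for thromboembolic events, thrombotic microangiopathy and anaphylaxis use exposure time and are not touched. The change should be made, because it is cheap and the sponsor cannot make it later from aggregate data.

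**What to change.** - In Section 8.7.2, count bleeds and set the offset over the period from first dose to the end of emicizumab exposure, and define that end date.
- Report the ABR over all follow-up since first dose beside it, as a sensitivity analysis.
- In the synopsis, name the negative-binomial ABR with a 95% CI as the estimate, as in Section 8.7.2 (adding the CI there), and label mean with SD as a descriptive summary.

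The cost is wording changes in two places and one additional end date in the registry's program. The on-drug analysis has slightly fewer person-years and may be affected by informative censoring if children stop because of bleeding. The all-follow-up analysis is there to show how much that could matter.
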